NCT03055260

Low Intensity Blood Flow Restriction Training Study

PI: [name]

Document Date: 2/1/2017

Effect of low intensity blood flow restriction training on lower extremity strength and hypertrophy

[name], DPT – Fairview/Institute for Athletic Medicine

Protocol v3.0 – February 1, 2017

Project Summary

This study is looking at the effect of blood flow restriction in the leg on overall strength gain and muscle increase. Subjects will complete baseline testing that will measure quadriceps muscle cross-sectional area via ultrasound technology, as well as complete 6 weeks of sessions (2 times per week) in which they perform controlled exercises, one leg at a time.

Subjects will be assigned to one of two groups: either the 1.) experimental group or 2.) control group. The experimental group will exercise with a blood flow restriction cuff around their right leg inflated to 100-250 mmHg (depending on participant size), and the control group will also exercise with a cuff on their right leg but with a pressure much less than that of the experimental group. Both groups however will complete the exact same protocol throughout the entirety of the study. Once the 6 weeks of training is up, muscle cross sectional area via ultrasound and 1RM will be re-tested and compared to the initial measurements.

Background

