Physically active individuals with the goal of increasing muscle mass and enhancing performance often turn to resistance training. Per the American College of Sports Medicine's recommendations, 70% of a person's 1 repetition maximum, for 6-12 repetitions, is required to induce hypertrophy in human skeletal muscle. Muscle loading below this 70% 1RM has shown to be less effective for muscle hypertrophy. Recent research over the past 5-10 years has shown that low load resistance training (30% of 1RM) combined with moderate blood flow restriction has resulted in muscle hypertrophy gains similar to the traditional high load training. Blood flow restriction consists of using blood pressure-like cuffs at the proximal portion of arms or legs with the purpose of restricting ~80% of arterial flow to the muscle and 100% of the venous return. This short-term (~5 minutes for entire protocol) decrease in blood flow has been theorized to work via increased: acute muscle cellular swelling, metabolic accumulation resulting in increased muscle fiber recruitment, growth hormone release, proliferation for myogenic stem cells, and enhanced signaling of protein synthesis. BFR has shown favorable results across populations, including elderly, trained athletes, and those recovering from injury who are not able to load their joints at 70% of their 1RM. It is currently being used in rehabilitation settings as well as in professional sports.

Study Purpose/Objective

The purpose of this study is to investigate whether the addition of blood flow restriction to low load exercise, will result in changes in quadriceps hypertrophy or lower extremity strength.

Inclusion Criteria

Male or female ages 18-49

Exclusion Criteria

Pregnant, hypertensive, recent back or lower extremity injury, history of blood clotting, varicose veins, adults lacking the capacity to consent for themselves

Methods and Procedures

Session 1: baseline testing

- 5-minute warm-up; 1RM calculation for both right and left legs using a supine leg press machine; cross-sectional measurement of both right and left quadriceps muscle using ultrasound technology.
- After day 1 testing; randomly allocate subjects to either control group or experimental group

Sessions 2-9: 6 weeks of exercise protocol, 2x/week

Both the experimental and control groups will complete the same protocol for the entirety of the study:

- 5- minute warm up

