- Using a single-leg press exercise machine: Subjects complete the testing protocol with either blood flow restriction (cuff inflated to 100-250 mmhg depending on size of person) or no blood flow restriction (placebo inflation) on right limb.
 - Protocol: 30 repetitions – 15 repetitions – 15 repetitions – 15 repetitions with each set separated by ~30 seconds.
 - Right and left legs will be alternating, but only right leg will have the occlusion cuff

Session 10: Re-test

- Re check 1RM, cross sectional area of quadriceps with ultrasound

Data Safety and Monitoring Plan

The PI will be responsible for monitoring and handling any potential problems that arise, including, but not limited to, informing the IRB immediately of any safety issues or concerns.

Injury

In the event that this research activity results in an injury, treatment will be available, including first aid, emergency treatment and follow-up care as needed. Care for such injuries will be billed in the ordinary manner to you or your insurance company. If you think that you have suffered a

research related injury, let the study administrators know right away. If serious injury were to occur, the PI will see to it that immediate medical attention is provided, including having the PI transport the subject to the nearest appropriate medical facility and/or contacting the appropriate emergency services.

Statistical Analyses

Independent Samples t-tests, Paired samples t-test, repeated measures ANOVAs and two-way ANOVAs will all be employed to determine difference within and between groups, across trials and conditions. SPSS v23 will be utilized for all statistical analyses.

Data and Record Keeping

The PI will be responsible for collecting and maintaining all data, and storing said data on a password-protected computer that will remain locked in a Fairview clinic office.

References

Loenneke, J. P., Wilson, J. M., Marín, P. J., Zourdos, M. C., & Bemben, M. G. (2011). Low intensity blood flow restriction training: A meta-analysis. *European Journal of Applied Physiology*, *112*(5), 1849-1859. doi:10.1007/s00421-011-2167-x

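### Baseline CSA and 1RM are measured before randomisation but no listed test adjusts for them, and the between-group t-test has no stated outcome value; a baseline-adjusted ANCOVA would settle this almost free

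*Combined protocol and SAP*

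**What the plan says.** Under Methods and Procedures, Session 1 consists of "1RM calculation for both right and left legs using a supine leg press machine" and "cross-sectional measurement of both right and left quadriceps muscle using ultrasound technology". Allocation follows: "After day 1 testing; randomly allocate subjects to either control group or experimental group". Both outcomes are measured once more, at Session 10. Only the right leg wears the occlusion cuff.

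The analysis plan is one sentence on methods and one on software (SPSS v23). The methods sentence states that "Independent Samples t-tests, Paired samples t-test, repeated measures ANOVAs and two-way ANOVAs will all be employed". The aim it gives for these tests is "to determine difference within and between groups, across trials and conditions". No covariate appears, and no test is tied to a dependent variable.

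Two other places bear on the question. The Project Summary says the outcomes "will be re-tested and compared to the initial measurements", and the Study Purpose/Objective asks whether adding restriction "will result in changes in quadriceps hypertrophy or lower extremity strength". Both lean towards an analysis of change. Neither says what the independent t-test is to compare.

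**The concern.** Values taken before randomisation are legitimate covariates, and for muscle size and strength they can be expected to predict the re-test value. None of the listed methods uses them that way. Baseline enters at most by subtraction: through the paired tests, or through the group-by-time term of the repeated measures ANOVA.

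Three things are at stake.

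- **Precision.** If the independent t-tests use re-test values, the between-person variation that baseline could explain stays in the comparison.
- **Chance imbalance.** With a given baseline difference between arms, a re-test comparison carries part of that difference forward, and a change-score comparison over-corrects for it.
- **Choice after the fact.** The plan says that all the tests will be used. The same data can therefore yield a re-test result and a change result for one question, with no rule for which one counts.

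**Working it through.** **Inputs.** From the documents: one baseline value before randomisation, one re-test value, two randomised groups, and the four listed test families. Not in the documents, so assumed: n per arm (10 to 30), 1:1 allocation, no dropout, two-sided alpha 0.05, a true effect of 0.5 SD, normal data, equal SD at both times (varied under the objection below), and baseline to re-test correlation r, mainly 0.7 to 0.9. The plan states no figure of its own to reproduce.

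**Step 1: what the repeated measures ANOVA tests.** With one pre and one post value, the group-by-time F equals the square of the t statistic for change. A numerical check gave 0.0043046 for both. The plan therefore contains a change-score comparison, but not a covariate-adjusted one.

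**Step 2: variances of the group difference, in SD² units.**

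- Re-test only: 2/n
- Change: (2/n) × 2(1 − r)
- ANCOVA: (2/n) × (1 − r²) × (2n − 3)/(2n − 4)

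The last factor is the cost of estimating the slope: 27/26 = 1.038 at 15 per arm and 17/16 = 1.063 at 10 per arm.

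**Step 3: ANCOVA against change.** The ratio is ((1 + r)/2) × (2n − 3)/(2n − 4). At n = 15 and r = 0.8 this is 0.90 × 1.038 = 0.935, a saving of about 7%.

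| n per arm | r = 0.7 | r = 0.8 | r = 0.9 | break-even r = (2n − 5)/(2n − 3) |
|---|---|---|---|---|
| 10 | 0.903 | 0.956 | 1.009 | 0.88 |
| 15 | 0.883 | 0.935 | 0.987 | 0.93 |
| 20 | 0.874 | 0.925 | 0.976 | 0.95 |
| 30 | 0.865 | 0.916 | 0.967 | 0.96 |

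Above the break-even r, ANCOVA is slightly less precise than change scores.

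**Step 4: ANCOVA against re-test only, n = 15.** The ratio is (1 − r²) × 1.038 = 0.530, 0.374 and 0.197 at r = 0.7, 0.8 and 0.9. The savings are 47%, 63% and 80%.

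**Step 5: power for 0.5 SD, n = 15 (simulation).**

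| r | re-test | change | ANCOVA |
|---|---|---|---|
| 0.7 | 26% | 40% | 44% |
| 0.8 | 26% | 55% | 58% |
| 0.9 | 26% | 84% | 84% |

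At lower correlations the ordering of the two t-tests can reverse. At 20 per arm and r = 0.3, power is 34% for re-test, 25% for change and 36% for ANCOVA.

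**Step 6: chance imbalance.** A one-standard-error baseline difference at n = 15 is √(2/15) = 0.365 SD. At r = 0.8 the conditional bias is +0.8 × 0.365 = +0.29 SD for re-test values and −0.2 × 0.365 = −0.07 SD for change. ANCOVA removes it, apart from error in the estimated slope.

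**Step 7: running both t-tests.** With no true effect, claiming success if either the re-test or the change t-test is significant gives a type I error of 8.9% to 9.7% per outcome (20 per arm, r from 0.5 to 0.95). ANCOVA stays at about 5%. With a 0.5 SD effect, 15 per arm and r = 0.8, the two t-tests disagree on significance in about 45% of trials.

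**The case against.** The strongest reply is that a valid between-group analysis using baseline is already listed. The repeated measures group-by-time test is a change-score comparison, and the summary and objective point the same way. Against that comparator the gain from ANCOVA is small. The large figures apply only if the t-tests use re-test values, which no section states. This stands as a limit on size. It does not remove the ambiguity, because the independent t-test is listed beside the repeated measures ANOVA and its outcome value is left open.

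The equal-SD assumption also matters. In general the conditional biases are +b and −(1 − b) times the baseline difference, with b = r × (re-test SD)/(baseline SD). At 15 per arm with the re-test SD 15% larger, the ANCOVA to change variance ratio is 0.98/1.02/1.03 at r = 0.7/0.8/0.9; with it 13% smaller, 0.74/0.78/0.78. The break-even correlations are therefore not fixed constants. The exposure is lopsided, though: ANCOVA loses about 3% of variance at worst in these cases and gains up to about a quarter.

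The correlation range cuts both ways. The modest loss from using change scores holds for r of about 0.7 or more. At r = 0.3 the large-sample relative variances are 1.40 for change and 0.91 for ANCOVA. At r = 0.5 the re-test and change analyses are equally precise.

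Finally, ANCOVA does not choose between CSA and 1RM as primary outcome, set alpha or give a multiplicity rule, and the two-way ANOVAs could still supply a competing between-group result. That is correct. Those gaps need their own decisions, and the fix should cover the two-way ANOVAs explicitly.

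**Conclusion.** The concern holds. That no covariate is named, and that the t-test's outcome value is unspecified, can be read directly from the plan and needs no assumption. The sizes are illustrative, because n, r, the SDs and the effect size are all absent from the documents.

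Against a re-test comparison, the gain from baseline adjustment is large when r is high. Against change scores it is modest, at 12%/7%/1% of variance for 15 per arm and r = 0.7/0.8/0.9 with equal SDs. In a very small trial with r of about 0.9 or more there is no gain: the worst equal-SD power loss found was about one point (90.3% against 91.3% at 10 per arm, r = 0.95). With r unknown, ANCOVA is the safer choice, and it gives one pre-specified estimate per outcome.

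This is a change the sponsor should make. It is not a fatal flaw, since randomisation leaves every option unbiased on average.

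**What to change.** Add to Statistical Analyses: for each outcome (CSA and 1RM), the between-group comparison is an ANCOVA of the right-leg re-test value on randomised group, with the same leg's Session 1 value as covariate, reported as an adjusted mean difference with 95% confidence interval.

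State that this replaces the independent t-test and the repeated measures group-by-time test for that comparison, and that no two-way ANOVA will serve as an alternative answer to the same question. Within-group paired tests and left-leg analyses can remain as secondary. If the sponsor regards both legs as the target of inference, the plan should say so and define the comparison accordingly.

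The cost is a sentence or two of text. The data are already scheduled for collection, and SPSS v23 fits the model. The statistical price is one residual degree of freedom plus the slope-estimation inflation: 3.8% of variance at 15 per arm and 6.3% at 10 per arm, already included in the ratios above.
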